3.4 Rationale for Romiplostim in CIT

At MSKCC, [name], [name], and [name] have treated over 50 patients with romiplostim for CIT. Our initial case series of 20 patients was published in 2014, indicating 19 of 20 treated patients meeting the goal of normalization of platelet count to >100,000/mcL ([name] et al, 2014).

Our interim observations of this current clinical trial suggests that romiplostim is effective and safe to improve platelet counts in patients with CIT. Of the treatment patients, 13 of the 14 (93%) romiplostim patients normalized their platelet count within the three-week primary endpoint. From our initial 21 patients who enrolled on this trial, 1 out of 7 (14.3%) observation patients have corrected her platelet counts within 3 weeks. (P= 0.0009 by two-tailed Fisher's Exact Test). Of the 5 observation patients who crossed over to romiplostim and were evaluable, all 5 corrected their platelet count within 3 weeks. Of all patients receiving romiplostim, 18 of 19 patients (95%) reach platelet counts of 100,000/mcL or greater within 3 weeks of treatment. No patients who resumed chemotherapy while receiving romiplostim (N=14) had a recurrence of CIT. We continue to see efficacy and safety within our patients currently on romiplostim. Based on highly significant efficacy and no further spontaneous correction of platelets, it was felt inappropriate to continue randomizing to the observation control arm.

No toxicity attributable to the romiplostim has been observed in our initial cases. Three of the initial 20 courses of treatment (19 patients) developed deep vein thrombosis which is within the historical range of between 10% and 30% ⁷ in comparable patients with metastatic cancer on chemotherapy. Further, one of the two patients with DVT had a previous history of DVT, prior to initiation of romiplostim, and had been off anticoagulation when the second thrombosis occurred.

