4.2 Intervention

I. Initial Phase of Study: Intervention For Primary Endpoint.

Romiplostim, n=60.

All patients will begin weekly romiplostim at 2 mcg/kg, subcutaneously. The romiplostim dose will be titrated as per Section 9.0, based on weekly CBC/platelet counts. For titration purposes, the target platelet count is 150,000-200,000/mcL.

II. Maintenance romiplostim, During Resumed Chemotherapy/Secondary Efficacy Endpoint

All patients on romiplostim who achieve a platelet count adequate (>100,000/mcL) and resume chemotherapy will be followed with continuation of weekly, titrated romiplostim.

In patients whose platelet counts have recovered within three weeks, we are observing for ability to resume 2 cycles (or eight weeks, whichever comes first) of cytotoxic chemotherapy without recurrence of chemotherapy-induced thrombocytopenia leading to chemotherapy dose delay or reduction; change in chemotherapy for progression of disease or other cancer related conditions; change in chemotherapy for other toxicities unrelated to thrombocytopenia; and death due to all causes. The duration for patients off chemotherapy will be noted. In addition we are also censoring patients who have tolerated chemotherapy with romiplostim support for up to 12 months.

Patients who are benefitting from the romiplostim, will be able to remain on treatment beyond the completion of 12 months on study, at the discretion of their oncologist and the study participating hematologist.

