11.0 TOXICITIES/SIDE EFFECTS

Based on our initial experience, we have not observed treatment-related toxicities in our first 40+ patients. Based on the romiplostim Prescribing Information, the most common adverse

reactions (≥5% higher patient incidence in romiplostim versus placebo) are arthralgia, dizziness, insomnia, myalgia, pain in extremity, abdominal pain, shoulder pain, dyspepsia, and paresthesia.

Individual cases of thrombosis and been reported in patients receiving romiplostim, but in one recent review of long-term use of romiplostim, "The thrombotic adverse event rate across all studies was 0.09 events per 100 patient-weeks on romiplostim therapy," markedly lower than would expected in patients with active cancer receiving chemotherapy. We have not observed an increased thrombosis rate compared with expected rates in patients with metastatic cancer, on chemotherapy, however, we will monitor any clinical evidence of thrombosis as well as hemorrhage.

Assessment of potential toxicity will be based on the Common Terminology Criteria for Adverse Events (CTCAE) Version 4.0. We will monitor for evidence of marrow toxicity, with weekly CBC (CBC must include: WBC, Hgb, platelet, MCV, cell differential) and lab toxicities of grade 3/4 will be adjudicated on a regular basis by the PI or Co-PI of the study. In addition, cytogenetics testing through bone marrow aspirate or peripheral blood will be performed within 30 days after the completion of the 4th month on treatment.

Patients will be monitored for Adverse Events throughout the study at the following time points: Toxicity Assessments will be completed at 3-weeks from enrollment (3-weeks from initiation of romiplostim in cross-over patients), and every 3 months while on romiplostim. A final toxicity assessment will be completed 1 month after the last dose of romiplostim. However, if the patient is discontinuing chemotherapy and going to hospice/ comfort care, the final toxicity assessment will be omitted if toxicities were managed regularly. For purposes of toxicity assessment, 3 months will be defined as 90 days +/- 15 days, 1 month is defined as 30 days +/- 15 days, and 3 weeks will be defined as 21 days + 9 days.

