Lastly, the frequency of thrombosis, marrow toxicity, and organ dysfunction will be tabulated.

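### Thrombosis is summarised only as an undefined frequency, with no time window or exposure, although time on romiplostim can run from about 3 weeks to beyond 12 months

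*Combined protocol and SAP*

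**What the plan says.** The closing line of Section 14.0 is the whole analysis plan for thrombosis: "Lastly, the frequency of thrombosis, marrow toxicity, and organ dysfunction will be tabulated". It does not say whether patients, courses or events are counted, over what period, with what denominator or with what interval. Sections 2.0 and 4.1 refer to safety at set times, and Section 11.0 lists them: 3 weeks, every 3 months on drug, and one month after the last dose. These are assessment times; no summary is attached to them.

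Time on drug is open-ended. Under the schema (Section 1.0) and Section 13.0, a patient below the platelet threshold at week 3 may leave or continue. Section 13.0 adds death, withdrawal, loss to follow-up and stopping of chemotherapy. Section 4.2 says that patients who benefit "will be able to remain on treatment beyond the completion of 12 months on study".

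The protocol uses two outside figures. Section 3.4 reports "Three of the initial 20 courses of treatment (19 patients) developed deep vein thrombosis" and places this within a historical 10% to 30%, with no follow-up time on either side. It then says "one of the two patients with DVT had a previous history of DVT". Section 11.0 quotes a review: "The thrombotic adverse event rate across all studies was 0.09 events per 100 patient-weeks on romiplostim therapy", and calls this "markedly lower than would expected in patients with active cancer receiving chemotherapy".

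**The concern.** Safety is the second secondary objective in Section 2.0, and thrombosis is the first adverse event named as a safety endpoint in Section 4.1. Since the observation arm was dropped (Section 14.0), outside figures are the main yardstick left, and the protocol already uses them to reassure. A percentage of patients mixes the risk per unit of time with how long patients stayed on drug. Two cohorts with the same hazard give different percentages if one stops earlier. A low figure could therefore reflect short exposure rather than low risk, and a reader of the planned table could not tell which.

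**Working it through.** **Inputs from the protocol.** 60 patients (Section 14.0); 3 DVTs in 20 courses, 19 patients, and the 10% to 30% range (Section 3.4); 0.09 events per 100 patient-weeks (Section 11.0); exposure from about 3 weeks (Section 1.0) to beyond 12 months (Section 4.2), so at least 52/3 = 17-fold.

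**Assumptions.** Mean time on drug is not given, so 3, 8, 13, 26 and 52 weeks are tried. A final count of 9/60 (15%) is chosen only because it matches 3/20. Hazards are taken as constant where stated.

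**1. The protocol's own figure.** 3/20 = 15% (exact 95% interval 3.2% to 37.9%), which lies inside 10% to 30%. With the two-patient wording, 2/19 = 10.5% (1.3% to 33.1%), also inside. The comparison reproduces on either count, but the intervals run past both ends of the range.

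**2. The percentage depends on early stopping.** Let the hazard give 15% at 52 weeks: h = −ln(0.85)/52 = 0.00313 per week. Risk by week 3 is 1 − exp(−3h) = 0.93%. If a fraction f stops at week 3 and the rest stay 52 weeks, the expected percentage is f × 0.93% + (1 − f) × 15%.

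| f | Percentage with thrombosis |
|---|---|
| 0 | 15.0% |
| 0.10 | 0.09% + 13.50% = 13.6% |
| 0.25 | 11.5% |
| 0.50 | 8.0% |
| 0.75 | 4.4% |

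The hazard is the same in every row.

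**3. One percentage, many rates.** Rate = 9/(60 × mean weeks) × 100, with exact Poisson limits, taking one event per affected patient.

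| Mean weeks | Patient-weeks | Events per 100 patient-weeks (95% interval) |
|---|---|---|
| 3 | 180 | 5.0 (2.3 to 9.5) |
| 8 | 480 | 1.9 (0.86 to 3.6) |
| 13 | 780 | 1.15 (0.53 to 2.2) |
| 26 | 1,560 | 0.58 (0.26 to 1.10) |
| 52 | 3,120 | 0.29 (0.13 to 0.55) |

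The span is 17-fold, so a percentage cannot be converted to the Section 11.0 scale without patient-weeks.

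**4. The 10% to 30% range needs a window.** If it were a 12-month figure (an assumption), a constant hazard would give 0.6% to 2.0% at 3 weeks and 2.6% to 8.5% at 13 weeks. A result of 15% would lie inside the 12-month range and above the 13-week range.

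**The case against.** The strongest reply has five parts.

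- The historical 10% to 30% is itself a proportion, and Section 3.4 already sets a proportion beside it. This stands. A reader might infer that the planned result can be compared with neither outside figure. For this one the comparison can be made; its weakness is that neither side states a window.
- The word used is frequency, and nothing commits the plan to a crude percentage. This stands too. The fault is an unspecified summary, not a stated wrong one.
- Safety is assessed at set times, and exposure is nearly uniform at 3 weeks. True, but Section 14.0 does not carry those times into any table, and exposure diverges afterwards.
- Neither outside figure is a planned comparator. Section 11.0 reports experience to date and then promises monitoring, and it expects cancer patients to exceed the quoted rate. The only matching entry in the reference list (reference 8) concerns chronic ITP. A reader might divide the rates in the second table by 0.09 and conclude that romiplostim carries many times the expected thrombosis risk. The documents do not support that: the populations differ and the exposure is assumed.
- Week-3 failures should be few, since Section 14.0 expects at least 90% success and Section 3.4 reports 18 of 19. This limits that one route: at 10% stopping, the illustrative figure only falls from 15.0% to 13.6%. Progression, death, withdrawal and the end of chemotherapy also shorten exposure, and the protocol gives no estimate of how often.

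**Conclusion.** The point holds as a gap in the analysis plan that should be closed. A tabulated frequency without unit, window or exposure cannot be read as a risk when time on drug may differ 17-fold or more. It cannot be compared with a rate per patient-week, and beside 10% to 30% it lacks a common time basis. The illustrative size is a fall from 15% to about 8% if half of the patients stop at week 3, and a range of 5.0 to 0.29 events per 100 patient-weeks for the same 9/60. Both rest on assumed exposure and an assumed count, and the first also on a constant hazard. The true distortion depends on exposure that the documents do not report.

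The finding does not show that thrombosis is increased, nor that the trial fails a test it set itself; no such test is planned. The 0.09 figure is context from another population, not a cancer benchmark.

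Two related matters affect the numerator. Section 11.0 limits reported toxicities to those not known to be linked to prior chemotherapy or underlying disease, so thromboses attributed to the cancer could be left out. Section 3.4 moves from three courses to two patients with DVT without explanation.

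**What to change.** In Section 14.0:

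- Keep the count of patients with thrombosis, and show the mean and range of time on romiplostim beside it.
- Add thrombotic events per 100 patient-weeks on romiplostim, first to last dose, with an exact Poisson 95% interval. Report events in the 30 days after the last dose separately, or put that time in both numerator and denominator. The choice matters: 30 days is about 4.3 weeks, and at a mean of 8 weeks it turns 9/480 = 1.9 into 9/(60 × 12.3) = 1.2 per 100 patient-weeks.
- Add the cumulative incidence of first thrombosis at 3, 6 and 12 months, with death as a competing event.
- Count all thromboses whatever their attribution, so that the Section 11.0 filter does not lower the numerator.

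In Sections 3.4 and 11.0, state the population and time basis of each outside figure, and reconcile the three courses with the two patients.

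The cost is small: a few lines of analysis text and one table. Section 16.0.3 already requires Treatment and Adverse Event forms, but it lists forms rather than date fields, so the sponsor should check that every thrombosis and its date is captured. With few events the intervals will be wide. No treatment or visit changes.

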15.0 RESEARCH PARTICIPANT REGISTRATION AND RANDOMIZATION PROCEDURES

15.1 Research Participant Registration

Confirm eligibility as defined in the section titled Criteria for Patient/Subject Eligibility.

Obtain informed consent, by following procedures defined in section entitled Informed Consent Procedures.

During the registration process registering individuals will be required to complete a protocol specific Eligibility Checklist.

The individual signing the Eligibility Checklist is confirming whether or not the participant is eligible to enroll in the study. Study staff are responsible for ensuring that all institutional requirements necessary to enroll a participant to the study have been completed. See related Clinical Research Policy and Procedure #401 (Protocol Participant Registration).

15.1.1 Registration for Participating Sites

Central registration for this study will take place at Memorial Sloan Kettering Cancer Center

To complete registration and enroll a participant from another institution, the site must contact the designated research staff at MSK to notify him/her of the participant registration.

Registration documents should be submitted per the contact information provided by the MSK study coordinator.

The following documents must be sent for each enrollment within 24 hours of the informed consent form being signed:

- The completed or partially completed MSK eligibility checklist
- The signed informed consent and HIPAA Authorization form
- Supporting source documentation for eligibility questions (laboratory results, radiology reports, MD notes, physical exam sheets, medical history, prior treatment records)

Upon receipt, the research staff at MSK will conduct an interim review of all documents. If the eligibility checklist is not complete or source documentation is missing, the participant will be registered PENDING and the site will be responsible for sending the completed registration documents within 45 days of the consent.

If the external registration submission is complete, the participating site IRB has granted approval for the protocol, and the site is in good standing, the MSK research staff will enter the completed registration documents to MSK CTMS for participant enrollment as stated in section 15.1.

Once the participant is registered, the participant will be assigned a number in the MSK Clinical Research Database (CRDB). This number is unique to the participant and must be written on all data and correspondence for the participant. This protocol participant number will be relayed back to study staff at the registering site via e-mail and will serves as the enrollment confirmation.

15.2 Randomization

There will be no randomization in this study.

16.0 DATA MANAGEMENT ISSUES

A Research Study Assistant (RSA) will be assigned to the study at MSKCC. The responsibilities of the RSA include project compliance, data collection, abstraction and entry, data reporting, regulatory monitoring, problem resolution and prioritization, and coordinate the activities of the protocol study team.

The data collected for this study will be entered into a secure database, CRDB. Source documentation will be available to support the computerized patient record.

Investigators will permit study-related audits by the sponsor, IRB review, and regulatory inspection(s) (e.g., FDA, EMEA, TPP), providing direct access to the facilities where the study took place, to the source documents, and to all other study documents.

16.0.1 Data and Source Documentation for Participating Sites

Data

The participating sites will enter data remotely into electronic Case Report Forms (eCRFs) using the internet based system CRDBi-Multicenter. Data entry guidelines have been generated for this study and the site staff will receive database training prior to enrolling its first participant. The participating

site PI is responsible for ensuring these forms are completed accurately in a timely manner. A schedule of required forms is shown in section 16.0.3

Source Documentation

Source documentation refers to original records of observations, clinical findings and evaluations that are subsequently recorded as data. Source documentation should be consistent with data entered into eCRFs. Relevant source documentation to be submitted throughout the study includes:

- Baseline measures to assess pre-protocol disease status (ex. CT, PSA, bone marrow)
- Treatment records
- Toxicities/adverse events that meet study reporting requirements not previously submitted with SAE reports
- Response designation

Source documentation should include a minimum of two identifiers to allow for data verification. MSK will maintain the confidentiality of any subject-identifiable information it may encounter.

16.0.2 Data and Source Documentation Submission for Participating Sites

Participating sites should enter data directly into CRDBi-Multicenter. Source documentation should be sent to MSK at the contact information provided by the MSK study coordinator. Submissions should include a cover page listing relevant records enclosed per participant.

16.0.3 Data and Source Documentation Submission Timelines for Participating Sites

Data and source documentation to support data should be transmitted to MSK according to the chart below.

Chart: Data and Source Submission Requirements and Timelines

	Baseline	Week 1	Week 2	Week 3	After Week 3	SAE	Off Study		
Submission Schedule	Submission Schedule								
Source Documentation	Within 24 hours (see section 15.1.1)	within 14 days of visit			Within 3 days of event (see section 17.2.1);	Within 14			
eCRFs	Within 7 days of visit	Within 14 days of visit				updates to be submitted as available	days of visit		
Required Forms									
Minimal Dataset	X						X		
Disease Form	X								
Physical Exam Form	Х								
Prior Therapy Form	X								
Concomitant Medications Form	X	Х	Х	Х	x				
Treatment Form		X	X	X	X				

Laboratory Form	Х	X	X	X	X		X
Diagnostic Test Form	Х						
Adverse Event Form*		Х	Х	Х	Х	Х	Х
Serious Adverse Event						Х	
Hospitalization Form						Х	

^{*}Toxicities/adverse events that meet reporting requirements as outlined in section 11

16.1 Quality Assurance

Weekly registration reports will be generated to monitor patient accruals and completeness of registration data. Routine data quality reports will be generated to assess missing data and inconsistencies. Accrual rates, the extent and accuracy of evaluations and follow-ups will be monitored periodically throughout the study period for potential problems, which will be brought to the attention of the study team for discussion and action.

Random-sample data quality and protocol compliance audits will be conducted by the study team, at a minimum of two times per year, or more frequently if indicated.

16.1.1 Quality Assurance for Participating Sites

Each site accruing participants to this protocol will be audited by the staff of the MSK study team for protocol and regulatory compliance, data verification and source documentation.

Audits will be conducted annually during the study (or more frequently if indicated) and at the end or closeout of the trial. Ideally the first audit will occur shortly after the first patients are enrolled. The number of participants audited will be determined by auditor availability and the complexity of the protocol. Each audit will be summarized and a final report will be sent to the PI at the audited participating site within 30 days of the audit.

16.1.1 Response Review

Since therapeutic efficacy is a stated primary objective, participant's responses are subject to review by MSKCC's Therapeutic Response Review Committee (TRRC). Radiology, additional lab reports and possibly bone marrow biopsies and/or aspirates will be submitted for MSKCC TRRC review and confirmation of response assessment.

16.2 Data and Safety Monitoring

The Data and Safety Monitoring (DSM) Plans at Memorial Sloan Kettering were approved by the National Cancer Institute in August 2018. The plans address the new policies set forth by the NCI in the document entitled "Policy of the National Cancer Institute for Data and Safety Monitoring of Clinical Trials."

There are several different mechanisms by which clinical studies are monitored for data, safety and quality. At a departmental/PI level there exists procedures for quality control by the research team(s). Institutional processes in place for quality assurance include protocol monitoring, compliance and data verification audits, staff education on clinical research QA and two institutional committees that are responsible for monitoring the activities of our clinical trials programs. The committees: *Data and Safety Monitoring Committee (DSMC)* for Phase I and II clinical trials, and the *Data and Safety Monitoring Board (DSMB)* for Phase III clinical trials, report to the Deputy Physician-in-Chief, Clinical Research.

The degree of monitoring required will be determined based on level of risk and documented.

The MSK DSMB monitors phase III trials and the DSMC monitors non-phase III trials. The DSMB/C have oversight over the following trials:

- MSK Investigator Initiated Trials (IITs; MSK as sponsor)
- External studies where MSK is the data coordinating center
- Low risk studies identified as requiring DSMB/C review

The DSMC will initiate review following the enrollment of the first participant/or by the end of the year one if no accruals and will continue for the study lifecycle until there are no participants under active therapy and the protocol has closed to accrual. The DSMB will initiate review once the protocol is open to accrual

16.3 Regulatory Documentation

Prior to implementing this protocol at MSK, the protocol, informed consent form, HIPAA authorization and any other information pertaining to participants must be approved by the MSK Institutional Review Board/Privacy Board (IRB/PB). There will be one protocol document and each participating site will utilize that document.

The following documents must be provided to MSK before the participating site can be initiated and begin enrolling participants:

- Participating Site IRB approval(s) for the protocol, appendices, informed consent form and HIPAA authorization
- Participating Site IRB approved informed consent form and HIPAA authorization
- Participating Site IRB membership list
- Participating Site IRB's Federal Wide Assurance number and OHRP Registration number
- Curriculum vitae and medical licenses for each investigator and consenting professional
- Documentation of Human Subject Research Certification training for investigators and key staff members at the participating site
- Documentation of Good Clinical Practice (GCP) training for the PI and co-PI at the participating site
- Participating site laboratory certifications and normals

Upon receipt of the required documents, MSK will formally contact the site and grant permission to proceed with enrollment.

Prior to implementing this protocol at MSK, the protocol, informed consent form, HIPAA authorization and any other information pertaining to participants must be approved by the MSK Institutional Review Board/Privacy Board (IRB/PB). There will be one protocol document and each participating site will utilize that document.

Participating sites that are conducting data analysis should submit this protocol to their IRB according to local guidelines. Copies of any site IRB correspondence should be forwarded to MSK

